Baseline data collection. The baseline assessment will be conducted via ACASI. The participant will first complete the Alcohol Use Disorders Identification Test (AUDIT) to assess eligibility into the study. The ACASI will automatically alert the assessor if the participant is eligible based on the hazardous alcohol use criteria. If eligible, the participant will complete the remaining measures: (1) Center for Epidemiological Studies-Depression Scale (CES-D); (2) Harvard Trauma Questionnaire (HTQ); and (3) the Alcohol, Smoking, and Substance Involvement Screening Test (ASSIST). All of these measures have previously been translated and used by our team in Zambia and the AUDIT, CES-D, and ASSIST measures have been formally validated. A research assistant will be available if there are any challenges with the ACASI. Additionally, we will use HIV clinic files to extract HIV-related data. These data are captured as part of HIV routine care in Zambia and include: (1) ART initiation date, (2) hepatitis B surface antigen, (3) most recent CD4+ count, (4) cumulative and past 6-month ART retention, defined by medication possession ratio (MPR; an objective pharmacy record metric that we have used previously) and (5) plasma HIV viral load (measured at CIDRZ Central laboratory using the Roche COBAS/Ampliprep platform).

Secondary eligibility criteria for the RCT. Following completion of the baseline assessment, ACASI will automatically alert the assessor if the participant is eligible for the pilot RCT via a built-in algorithm. Criteria for the RCT will be (a) AUDIT scores that indicate a moderate-to-severe AUD ( $\geq 12$  for women;  $\geq 16$  among men) and/or (b) meeting validated symptom criteria for depression ( $\geq 16$  on CES-D), trauma/anxiety ( $\geq 2.5$  on HTQ), and/or substance use ( $\geq 27$  for any non-tobacco substance on ASSIST).

Randomization. Participants eligible for the pilot RCT will be randomized 1:1, stratified by sex, to receive the BI alone or BI+CETA. Participants who are NOT eligible for the pilot RCT will be provided with a BI but will not be randomized.

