Follow-up assessments. Alcohol and comorbidities will be assessed in all participants at 6 months (i.e., endline) after baseline. The ACASI questionnaire that was used at baseline will again be administered at this follow-up visit (i.e., the questionnaire at this visit is the same as at baseline). In addition to ACASI assessments, we will confirm self-reports of alcohol abstinence on the AUDIT by conducting a urine-based rapid alcohol biomarker test, ethyl glucuronide (uEtG). Finally, at the 6-month post-assessment, which coincides with a regularly scheduled clinic visit, we will extract relevant information from the client's HIV clinical record (this will be the same information that is collected at baseline), including: , (1) hepatitis B surface antigen, (2) most recent CD4+ count, (4) cumulative and past 6-month ART retention, defined by medication possession ratio (MPR; an objective pharmacy record metric that we have used previously) and (4) plasma HIV viral load (measured at CIDRZ Central laboratory using the Roche COBAS/Ampliprep platform). We will not collect any additional biospecimens for purposes of the study—all HIV-related data will be captured via chart extraction. To supplement retention data captured through MPR measurement, we will also assess visit adherence, the percentage of assigned pharmacy and clinical visits that were made (coming to clinic within 3 days).

Implementation data collection. We will conduct a mixed methods process evaluation with stakeholders involved in the CETA referral and treatment process, including follow-up FGDs and KIIs with participants from Stage 1A and CETA counselors. We will also conduct mixed methods interviews with approximately N=30 PLWH who participated in the Stage 1B pilot RCT. This will include a purposeful sample of PLWH from a range of ages and both sexes who did and did not complete the BI and CETA. Implementation factors to be explored will include: acceptability, appropriateness, reach, cost, feasibility, and sustainability and will explore the attitudes, thoughts, feelings, and barriers and facilitators related to implementation. Interviews will include an in-depth interview component and JHU quantitative implementation measures.

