Study Phase	Activity	Year 1				Year 2				Year 3			
		Q 1	Q 2	Q 3	Q 4	Q 1	Q 2	Q 3	Q 4	Q 1	Q 2	Q 3	Q 4
Planning	Study protocol finalization and ethical approval												
	Staff hiring and site preparation												
	Training of qualitative data staff												
Stage 1A	Focus groups and key informant interviews												
	Adaptation of CETA for PLWH												
	Development of CETA protocol in HIV care based on Stage 1A												
	CETA/mhGAP-IG trainings, assessor trainings, M&E trainings												
Stage 1B	CETA pilot cases												
	Recruitment, consent, screening and baseline assessments (ACASI, HIV)												
	Interventions active												
	Post-treatment assessments (ACASI, UEtG)												
	6-month outcomes assessment (ACASI, UEtG, HIV outcomes via chart review)												
Analysis, dissemination, and next steps	Implementation data collection (PLWH, clinic staff, policy officials)												
	Data analysis												
	Report/manuscript writing and dissemination at conferences												
	Preparation and submission of follow-up R01												

- Provide a brief data analysis plan and a description of variables to be derived.

*Analysis of treatment uptake and completion.* We will estimate a logit model with a binary outcome (1=completer; 0=non-completer) to assess predictors of treatment completion. Predictors will be demographic (e.g., sex, age), clinical (e.g., symptom severity), and structural (e.g., distance from clinic) level factors.

*Analysis of ACASI outcome data.* Analyses will be intent-to-treat. AUDIT score, along with other continuous secondary outcomes (Past 30-Day TLFB [% days drinking and mean drinks per day], CES-D, HTQ, ASSIST scores) will be modelled with linear mixed models. Fixed effects will include treatment arm (0=BI; 1=BI+CETA), time (0=Baseline; 1=6-months post-baseline), and interaction terms between treatment arm

and time. This will allow estimation of the mean difference in change in score between arms and 95% confidence intervals. Cohen's D will be calculated to estimate effect size. Covariates will be included if they differ meaningfully at baseline or predict significant change in the outcome. For dichotomous outcomes or non-normally distributed continuous outcomes, generalized linear mixed effects models will be estimated. Paired t-tests will be used to assess within group change among the non-Pilot RCT hazardous drinkers.

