*Analysis of CETA clinical monitoring data.* We will conduct longitudinal data analysis with CMF and TLFB daily estimates of drinking during CETA. Exploratory analysis will examine trajectories of weekly symptom change based on CMF score and number of drinks per day using spaghetti and scatter plots. We will explore the association between baseline client characteristics on symptom trajectories. We will use survival analysis to calculate the number of sessions required for 25%, 50%, and 75% of clients to achieve one or two standard deviation(s) in symptom improvement from baseline. We will also calculate the percentage of clients that achieve these changes by the end of treatment. Collectively, these analyses will provide insight into *when* symptoms change over the course of treatment, which may be useful in refining CETA in future studies.

*Analysis of HIV outcome data.* In both RCT and non-RCT participants, we will use a linear model to investigate changes to MPR during the period before and after the intervention and a logistic model for changes to the proportion with HIV viral suppression (defined as <1000 copies/ml, the standard in SSA). We will compare visit adherence between those randomized to BI+CETA versus BI alone. Because of the relatively small sample sizes in this pilot study, these data will be primarily descriptive; however, these data will inform a follow-up grant.

*Analysis of uEtG results.* The purpose of uEtG testing is to confirm abstinence and not to validate AUDIT scores >0. Based on Preliminary Studies we expect to identify 'under-reporters,' defined as participants who report abstinence on AUDIT or TLFB and test uEtG-positive. In a secondary analysis, we will exclude under-reporters and re-assess the impact of the intervention on alcohol use and other outcomes.

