The only biospecimen being collected in this study will be a urine ethyl glucuronide (ETG) test to confirm alcohol abstinence. In previous alcohol research conducted by our team in Zambia, we have found that it is important to compare self-reported alcohol use to an objective biomarker. This urine specimen will only be collected at one timepoint among cohort and RCT participants: at the 6-month post-baseline assessment. The test requires the participant to provide a small urine sample (appx. 100ml). During the study visit we will provide participants with a urine cup and ask them, in a private bathroom at the clinic, to provide us with a 100ml sample of urine. Following the sample collection, a study assessor will insert a dipstick into the sample and within 1 minute the test provides a qualitative (positive/negative) result for alcohol consumption within the past 2-5 days.

We will provide participants with results of the EtG test at the visit. No additional tests except the dipstick will be conducted with the sample. Following testing, the sample will be destroyed. We have used EtG tests previously with similar patient populations and it was found to be feasible and acceptable ([name] et al., 2018).

3. If genetic/genomic analyses are planned, address whether the data will be contributed to a GWAS or other large dataset. Address returning unanticipated incidental genetic findings to study participants.

N/A

4. If clinical or laboratory work will be performed at JHU/JHH, provide the JH Biosafety Registration Number.

N/A

5. If you will perform investigational or standard diagnostic laboratory tests using human samples or data, clarify whether the tests are validated and/or the lab is certified (for example is CLIA certified in the U.S.). Explain the failure rate and under what circumstances you will repeat a test. For all human testing (biomedical, psychological, educational, etc.), clarify your plans for reporting test results to participants and/or to their families or clinicians. Address returning unanticipated incidental findings to study participants.

The urine dipstick ETG test has been FDA-approved and validated.

Urine dipstick results (positive or negative) for ETG will be discussed with participants as soon as they are available (within 1 minute of sample collection).

6. If your study involves medical, pharmaceutical or other therapeutic intervention, provide the following information:

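### The only planned uEtG analysis drops biomarker-positive abstinence-reporters instead of counting them as drinkers, and its TLFB limb rests on conflicting text

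*Combined protocol and SAP*

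**What the plan says.** All references are to the combined protocol and SAP, Section V (Study Procedures) unless stated.

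- **Analysis of uEtG results.** The stated aim is: "The purpose of uEtG testing is to confirm abstinence and not to validate AUDIT scores >0". Under-reporters are "participants who report abstinence on AUDIT or TLFB and test uEtG-positive". The only analysis that follows is: "In a secondary analysis, we will exclude under-reporters and re-assess the impact of the intervention on alcohol use and other outcomes".
- **Follow-up assessments.** This paragraph ties the test to one instrument: "we will confirm self-reports of alcohol abstinence on the AUDIT by conducting a urine-based rapid alcohol biomarker test". It also says that "the questionnaire at this visit is the same as at baseline".
- **Baseline data collection.** After the AUDIT screen, "If eligible, the participant will complete the remaining measures". The measures then named are the CES-D, HTQ and ASSIST. No TLFB is listed.
- **Clinical monitoring data collection.** A past 7-day TLFB is taken in CETA sessions. The paragraph states that neither BI-alone nor cohort participants complete the TLFB.
- **Analysis of ACASI outcome data.** Analyses are by intent to treat. A 30-day TLFB is nevertheless among the continuous secondary outcomes modelled by arm and time.
- **uEtG timing.** The biospecimen item says: "This urine specimen will only be collected at one timepoint among cohort and RCT participants: at the 6-month post-baseline assessment". Table 4 has a row reading "Post-treatment assessments (ACASI, UEtG" and a separate row for the 6-month assessment that also names uEtG.

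Section III.B makes the change in AUDIT score to 6 months the primary endpoint. Abstinence is not a named outcome.

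**The concern.** The test is done after randomisation and measures the behaviour under study. Removing those who deny drinking and test positive therefore selects the analysis set on something close to the outcome. The people removed are known drinkers, so the remaining set overstates abstinence in each arm, and by more in the arm with more denial. The same exclusion is extended to other outcomes, where misreported drinking was not the problem to begin with.

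The stated aim is to confirm abstinence, yet no analysis compares confirmed abstinence by arm. The trial's one objective check on self-reported drinking is used only to take participants out.

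The definition also cannot be programmed as it stands. If the clinical-monitoring paragraph governs, only BI+CETA participants can be removed through the TLFB limb. If the ACASI analysis paragraph governs, the limb works in both arms, but the 30-day TLFB appears in no described assessment.

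**Working it through.** **Inputs from the documents.** Section III.B: 80 randomised per arm and 20% loss, so 80 × 0.80 = 64 completers per arm. A two-sided t-test at 5% with 80% power and d = 0.5 needs 63.77, rounded up to 64, so the plan's own 128 and 160 reproduce.

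**Assumed inputs.** No denial rate, abstinence rate, AUDIT SD or test accuracy is given. Let a = true abstinent share, x = share of the arm that drinks but reports abstinence, and s = uEtG sensitivity among deniers. Specificity is 100% unless stated.

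- Self-report: a + x
- Counting positives as drinkers: a + x(1 − s)
- Exclusion: [a + x(1 − s)] / (1 − xs)

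**Abstinence, BI+CETA minus BI, in percentage points**

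| Assumed case | Truth | Self-report | Exclusion | Counting |
|---|---|---|---|---|
| a = 25% both; x = 20% v 10%; s = 100% | 0 | +10.0 | +3.5 | 0 |
| x = 30% v 10% | 0 | +20.0 | +7.9 | 0 |
| x = 10% v 20% | 0 | -10.0 | -3.5 | 0 |
| x equal | 0 | 0 | 0 | 0 |
| x = 20% v 10%; s = 75% | 0 | +10.0 | +5.6 | +2.5 |
| x = 20% v 10%; s = 50% | 0 | +10.0 | +7.3 | +5.0 |
| a = 35% v 25%; 26.7% of drinkers deny in both arms; s = 100% | +10.0 | +7.3 | +11.1 | +10.0 |

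Worked lines:

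- First row: self-report is 45.0 v 35.0. Exclusion is 25/0.80 = 31.25 v 25/0.90 = 27.78.
- 75% sensitivity: counting is 30.0 v 27.5. Exclusion is 30.0/0.85 = 35.29 v 27.5/0.925 = 29.73.
- Last row: x = 0.65 × 0.267 = 17.3% v 0.75 × 0.267 = 20.0%. Self-report is 52.3 v 45.0. Exclusion is 35/0.827 = 42.3 v 25/0.80 = 31.25.

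A wider grid with no true effect (true abstinence 10-30%; denial among drinkers 5-10% in BI v 15-40% in BI+CETA) gives a false difference under exclusion of 1.1 to 9.4 points.

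**AUDIT score** (first row; drinkers average 14, abstainers and deniers score 0, SD 8):

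- Self-report: 0.55 × 14 = 7.70 v 0.65 × 14 = 9.10, difference -1.40.
- Exclusion: 7.70/0.80 = 9.63 v 9.10/0.90 = 10.11, difference -0.49. Truth is 0.
- Remaining numbers: 64 × 0.80 ≈ 51 v 64 × 0.90 ≈ 58. SE = 8 × √(1/51 + 1/58) = 1.54, and 0.49/1.54 ≈ 0.3.

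**Non-alcohol outcomes** (drinkers score 4 points above abstainers): 4 × (0.55/0.80 − 0.65/0.90) = -0.14. The full set has no bias from this source.

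**Precision of confirmed abstinence:** 1.96 × √(2 × 0.25 × 0.75/64) = 0.150, a half-width of about 15 points.

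**The case against.** The case for leaving the plan alone is a fair one. The exclusion is labelled secondary, stands beside an intent-to-treat analysis, and decides nothing. In the first case above it removes about 65% of the self-report bias on both scales (10.0 to 3.5; 1.40 to 0.49). Abstinence was never a named outcome, so a comparison of it is an addition. Differential denial is assumed throughout. ACASI, a different follow-up assessor and weekly safety calls to BI participants should limit it. All of this stands, and it holds the severity down. It does not rule out unequal denial, and it gives no reason to discard detected drinkers when the same data allow them to be counted.

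Four stronger readings are tempting, and the documents do not support them.

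- **That the TLFB limb applies to BI+CETA only.** The sentence restricting the TLFB sits in the paragraph on session forms and may concern that 7-day form alone. The 30-day version is listed for both arms. The text conflicts; it does not settle the matter.
- **That exclusion is worse than no correction.** Fixing denial at 20% of each arm with 35% v 25% truly abstinent gives exclusion +12.5 and self-report +10.0. But that implies denial by 0.20/0.65 = 30.8% v 0.20/0.75 = 26.7% of drinkers, so it is not equal denial. With equal denial per drinker, exclusion (+11.1) is nearer the true +10.0 than self-report (+7.3).
- **That the exclusion lacks a missing-data rule.** It removes only those who report abstinence and test positive, so an untested participant is not removed. The rule is needed for the added abstinence outcome.
- **That Table 4 proves a second urine test.** Its quarter shading is not readable in the text, and the follow-up and biospecimen text describes one 6-month collection. This is a small inconsistency to tidy.

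**Conclusion.** The point holds at minor to moderate severity. The plan states a rule that selects on a post-randomisation, outcome-related result and discards drinkers whom the test has identified. In every case computed, counting them is at least as close to the truth as excluding them. The gap is 3.5 points in the 20% v 10% case and 1.1 points in the true-effect case. With no true effect and equal denial there is nothing to correct. When the test misses deniers, counting is biased too, but less: +2.5 v +5.6 points at 75% sensitivity.

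These sizes rest entirely on assumed rates, and the direction depends on which arm denies more. On the AUDIT scale the residual is small. A reader might infer that the trial's main result is compromised; it is not, because the intent-to-treat AUDIT analysis does not use the exclusion.

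The TLFB conflict depends on no assumed rate. Until it is resolved, the exclusion can be read either as the same rule in both arms or as one with an extra route in BI+CETA.

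**What to change.** 1. Reconcile the baseline, follow-up, clinical-monitoring, ACASI-analysis and uEtG-analysis paragraphs on who completes a TLFB, which version and when. Define under-reporters only by a 6-month self-report collected in both arms: the AUDIT, plus the 30-day TLFB only if it is confirmed for both. State which AUDIT response counts as reported abstinence; the uEtG paragraph suggests a score of 0. As a minor point, reconcile Table 4 with the biospecimen item on uEtG timing.
2. Add uEtG-confirmed abstinence by randomised arm, as a secondary or exploratory estimate with its interval. Abstinent means reported abstinence and a negative test. Positive deniers, and all who report drinking whether tested or not, count as non-abstinent. State a rule for no 6-month self-report, or reported abstinence without a test: for example, multiple imputation by arm and sex with baseline AUDIT, varied by counting all such participants as non-abstinent.
3. Report uEtG positivity and denial by arm.
4. Do not apply the exclusion to CES-D, HTQ, ASSIST or HIV outcomes. If it is kept for alcohol outcomes, label it exploratory.

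The cost is wording and one derived binary variable from data already planned. The downsides are real:

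- It is one more outcome the trial was not sized for (half-width about 15 points).
- False-positive dipsticks count as drinking. At 95% or 90% specificity a true +10.0 becomes 0.95 × 10 = +9.5 or 0.90 × 10 = +9.0.
- The window is only 2-5 days, so earlier drinking is missed.
- The missing-data rule is itself an assumption. At 25% true abstinence in both arms, counting all missing as non-abstinent gives 25 × (0.75 − 0.85) = -2.5 points if loss were 25% v 15%, and 0 at 20% in both.

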### A. **Recruitment Process:**

1. Describe how you will identify, approach, and inform potential participants about your study. Include details about who will perform these activities and what their qualifications are.

Before any data collection begins, community meetings will take place at each site in order to explain the procedures of the study, the risk and benefits, the confidentiality of results, and to allow for any questions. Based on our prior experience using this approach in Zambia, which has featured good relationships with the local population, we do not anticipate difficulties in obtaining community approval.

- Stage 1A: CETA Adaptation

PLWH study participants for Stage 1A will be recruited from their regular care providers at the study HIV clinics in Lusaka. Care providers will be asked to inform their adult patients with a history of alcohol use while on ART about the presence of the qualitative study using a recruitment script (included with this IRB application). Interested participants will be referred to our on-site study assessor. The assessor will explain the study in full and obtain informed consent if the participant is interested. The assessor will obtain contact information from the participant to schedule the focus group discussion, which will happen at a later date. This method will ensure that only patients who express interest in the study to their usual care provider will have any contact with research staff.

Health worker and policy level participants will be contacted by a study assessor and informed about the qualitative study. Due to our team’s ongoing collaborative work with the study clinics and the Ministry of Health, we have an existing sampling frame of stakeholders who we will ask to participate in focus group discussions and key informant interviews. Our study team will contact these stakeholders about participation and explain the purpose of the study. If potential participants are interested, the assessor will obtain informed consent and participant contact details to set up the focus group discussion or key informant interview.

- Stage 1B: Pilot RCT of CETA

Study participants for the pilot RCT will be recruited from two HIV clinics in Lusaka. Participants will be recruited from the general HIV+ patient population at these clinics. While receiving regular care at these HIV clinics, clients will be informed of the pilot RCT by a care provider, which may be their physician, nurse, a

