### Interventions

- World Health Organization mhGAP BI. All participants (regardless of whether RCT criteria are met) will receive a BI. We will provide training to lay counselors (e.g., counselors/nurses already working in the HIV clinics) based on World Health Organization (WHO) mhGAP-Intervention Guide (mhGAP-IG). The mhGAP-IG was developed to provide non-specialists in LMIC with knowledge and skills to deliver low-intensity interventions with fidelity in primary care to treat mental, neurological, and substance use problems. WHO has developed modules to train health care workers. The JHU clinical team in Zambia will adapt these modules to provide a 2-day workshop for counselors at our two clinics. Training will cover components such as: (1) psychoeducation (e.g., examples of ways that hazardous use can be reduced); (2) engagement (e.g., discussing motivations for drinking); (3) personalized feedback and advice (e.g., helping the participant reflect on how use is impacting their life); and (4) encouragement for the participant to change their pattern of use.

Following the baseline assessment, the assessor will notify the on-duty counselor who has been trained in the BI. The BI, which is expected to take 10-15 minutes, will be offered to participants the same day and provided in a private room.

- [Common Elements Treatment Approach \(CETA\)](#). Lay counselors (e.g., HIV peer educators, counselors in the HIV clinics) will be trained to deliver CETA to participants randomized to BI+CETA (i.e., n=80). After enrollment, participants receiving CETA will flexibly meet with their counselor weekly for approximately one-hour sessions, for 6-12 weeks depending on presentation and symptom level. Core elements of CETA sessions are described in Table 2 and will be adapted as needed in Stage 1A.

**Table 2.** Common Elements Treatment Approach

Component	Content	Target
Engagement	Discuss how program helps Identify obstacles to engagement	Promote client buy-in
Safety	Assess client risk for harm to self/others Domestic violence/abuse assessment Initiate safety plan as needed	Assess and address client safety
Empirically-supported cognitive-behavioral elements		
Psychoeducation/Introduction	Program information, normalize symptoms, goal setting	Psychoeducation Reduce stigma

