CBT for alcohol and other substance use	CBT and MI integrated element to set goals and reduce use; Identification and strategies for addressing drivers of use	Reduce alcohol/substance use Increase social support
Behavioral Activation	Identify and engage in pleasurable activities	Reduce depressive symptoms; Facilitate engagement in helpful programs
Cognitive Coping/Restructuring	Identify and correct thoughts, feelings, and behaviors Replace unhelpful thoughts with helpful ones	Reduce depressive, anxious, and trauma-related symptoms; Reduce self-blame and stigma; Reduce negative thoughts on HIV care
Relaxation	Breathing exercises, imagery	Reduce anxiety and stress-related symptoms
Exposure	Talk about trauma memories or confront fears using gradual desensitization	Reduce trauma and anxiety symptoms
Problem Solving	Teach a process of steps to solve problems and make healthy decisions	Promote health decision making Skills training for problem solving

CETA will be delivered within the clinic with an option for community-based delivery (i.e., in a local church or community center) if preferred by the participant, similar to previous Zambia studies. To estimate uptake of CETA in a “real-world” HIV clinic setting, if participants do not attend their initial meeting, counselors will make several phone follow-ups for up to a maximum of 1 month after enrollment. If the participant does not start treatment within one-month post-enrollment, the counselor will cease efforts to engage them in CETA as additional retention efforts would be impractical in a non-research setting. After the initial session, if a client misses a follow-up appointment, the counselor will again follow-up by phone up to three times in a week and make a one-time home visit to re-engage the client. The research team will not contact the participant during the active intervention phase so as not to artificially influence the participant to attend CETA sessions.

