*Analysis of implementation data.* Mixed methods analysis based on NIH best practice guidelines will be used to integrate findings from the quantitative and qualitative data. Descriptive analyses will be used to investigate the quantitative data on constructs of acceptability, appropriateness, reach, feasibility, and cost. The qualitative data will provide in depth understanding of factors related to (1) mechanisms of change; and (2) barriers and facilitators to program implementation in the Zambian context. Findings will be shared with local (HIV clinics, Lusaka district, and Zambia MoH) and international stakeholders (PEPFAR/CDC, UNAIDS, etc.) to inform future programming efforts.

5. **Answer the following if they are relevant to your study design:**

1. If the study has different arms, explain the process for assigning participants (intervention/control, case/control), including the sequence and timing of the assignment.

The assessor will have two locked cabinets at the clinic with sealed envelopes. One cabinet will contain randomization assignments for female participants, the other for male participants. Printed on the outside of the sealed envelopes will be a Randomization ID. When a participant is eligible for the pilot RCT, the assessor will retrieve the next available envelope and record the Randomization ID and Screening ID on a Screening Information Sheet, thus linking the two IDs to the participant. Randomization IDs will be assigned to BI+CETA or BI alone using *randomize* in Stata *a priori* by a U.S.-based statistician not affiliated with the study. Randomization IDs will be randomized 1:1 in blocks of 20 stratified by sex. The assessor will inform the participant of their assignment by opening the envelope

immediately after the baseline assessment. This ensures that the assessor is blinded to the participant's randomization status during the assessment itself. Follow-up assessments will be conducted by a different assessor.

2. If human biospecimens (blood, urine, saliva, etc.) will be collected, provide details about who will collect the specimen, the volume (ml) and frequency of collection, how the specimen will be used, stored, identified, and disposed of when the study is over. If specimens will be collected for use in future research (beyond this study), complete the "Biospecimen Repository" section below.

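### Randomisation is stratified by sex but not by clinic, and the primary model names neither, so clinic balance in a two-clinic trial is not guaranteed by design or fixed in the analysis

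*Combined protocol and SAP*

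**What the plan says.** The recruitment section (V.A, Stage 1B) sets the trial at two sites: "Study participants for the pilot RCT will be recruited from two HIV clinics in Lusaka". The randomisation paragraph under Stage 1B reads "Participants eligible for the pilot RCT will be randomized 1:1, stratified by sex, to receive the BI alone or BI+CETA", and the Stage 1B overview likewise names only sex. The assignment process (Section V, item 5.1) adds the block size, "Randomization IDs will be randomized 1:1 in blocks of 20 stratified by sex", and the mechanics: "The assessor will have two locked cabinets at the clinic with sealed envelopes". Those cabinets are divided by sex, not by site, and for each person found eligible "the assessor will retrieve the next available envelope".

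Nowhere does the plan say whether each clinic has its own sequence, whether whole blocks go to one clinic, or how a single list per sex would serve two sites.

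Much of the care is tied to the clinic. The BI is given by trained staff such as counselors or nurses already employed there. On CETA the plan says "CETA will be delivered within the clinic with an option for community-based delivery".

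The data analysis plan for the ACASI outcomes specifies a linear mixed model with arm, time and arm-by-time as fixed effects. Other covariates are added only if the arms turn out to differ on them at baseline or if they prove to predict change. Neither clinic nor sex is named.

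**The concern.** Clinic is a plausible source of outcome differences, because patients, routine HIV care and counselors may differ between the two sites. With sex as the only stratum, the design guarantees arm balance within sex but not within clinic. If more of one clinic's participants land in one arm by chance, part of any between-clinic difference in AUDIT change is carried into the estimated CETA effect.

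The usual second line of defence is a prespecified clinic term, and it is also absent. A rule that adds covariates after looking at the data leaves open whether clinic will be in the primary model. The same rule leaves out sex, although sex was used to stratify. At stake are the precision and readability of one small trial meant to inform a larger one, not the validity of the randomisation.

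**Working it through.** **Inputs from the plan.** Section III.B: target effect d = 0.5, alpha 0.05, power 80% (written there as beta), 128 evaluable, 20% dropout, 160 randomised. Section V, item 5.1: 1:1 allocation, blocks of 20, sex strata. Section V.A: two clinics.

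**Assumptions, because the plan gives no figure.** Clinic split 50:50 (70:30 as a check); sex split 80/80 or 107/53 men/women, or 50% or 30% women; between-clinic difference in AUDIT change of 0.2 to 0.5 SD.

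**1. The plan's own sample size.** A two-sided two-sample t-test at d = 0.5, alpha 0.05 and 80% power needs 63.8, so 64 per arm, or 128 in total. Then 128 / (1 − 0.20) = 160. Both figures reproduce, and nothing below changes them.

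**2. Clinic gap if both clinics' participants are interleaved on one list per sex.** Allocation is then close to independent of clinic. For clinic share p and 80 per arm, SD = √[p(1 − p)(1/80 + 1/80)].
- p = 0.5: √(0.25 × 0.025) = 0.079, or 7.9 points.
- p = 0.7: √(0.21 × 0.025) = 0.072, or 7.2 points.
- Chance of a gap above 10 points at p = 0.5: 0.10 / 0.079 = 1.27 SDs, two-sided about 0.21.

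Simulation with blocks of 20 agrees.

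**3. The same quantity under other ways of dividing the envelopes** (simulated, N = 160, clinics 50:50):

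| How lists reach the clinics | SD (points) | 95th percentile | Chance of gap above 10 points |
|---|---|---|---|
| One list per sex, clinics interleaved | 7.9 | 15 | about 20% |
| Envelopes dealt alternately to the clinics | 7.7–8.1 | 15–16 | 19–22% |
| Each list cut into two contiguous stacks, ignoring block ends | about 3 | 5–6 | about 0.2% or less |
| Separate clinic-by-sex lists, blocks of 20 | 2.1–2.5 | 4–5 | essentially nil |

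The contiguous-stack row moves a little with where in a block the cut falls.

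**4. Effect on the estimate.** Shift = (clinic difference in AUDIT change) × (gap in clinic share).
- Gap of 15 points: 0.2 × 0.15 = 0.03 SD; 0.5 × 0.15 = 0.075 SD. Against 0.5, these are 6% and 15%.
- Gap of 6 points (contiguous stacks, 95th percentile): 0.2 × 0.06 = 0.012 SD; 0.5 × 0.06 = 0.03 SD.
- Gap of 5 points (clinic-by-sex lists, 95th percentile): 0.2 × 0.05 = 0.01 SD; 0.5 × 0.05 = 0.025 SD.

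**5. Where the precision gain comes from.** With equal clinics, clinic explains 0.25 × δ² of outcome variance, where δ is the clinic difference in SD units: 0.25 × 0.04 = 1% at 0.2 SD and 0.25 × 0.25 = 6.25% at 0.5 SD. That is 1.6 to 10 participants out of 160. A model term recovers it, with or without stratified lists. The term has to be clinic-by-time: a clinic main effect shifts baseline and follow-up equally, so with complete data it leaves the arm difference in change untouched.

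**6. Cost in arm sizes.** Up to four final blocks may be unfinished instead of two. The mean difference in arm size was about 2 participants with sex lists and 2.5 to 3 with clinic-by-sex lists; the largest simulated with clinic-by-sex lists was 16. Power at d = 0.5 with 128 evaluable is 80.1% at 64:64, 80.0% at 60:68 and 79.5% at 56:72.

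**The case against.** The strongest reply is that the envelopes must physically sit somewhere. If each clinic has its own pair of cabinets, whole blocks may already be sent to each, which would be stratification by clinic in all but name. Even a crude contiguous cut leaves an SD of about 3 points, and separate lists improve little on that. This stands as far as it goes. The text neither states such a procedure nor excludes it, so a reader who infers a one-in-five risk of a gap above 10 points would be treating the interleaved case as the expected one. The documents do not support that. Equally, they do not support assuming the benign case.

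It can also be said that the shift figures rest on an assumed clinic difference, since the plan reports none, and that 0.5 SD is as large as the whole target effect. That is correct, and it is why a range is given.

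Finally, the covariate rule might pick up a large clinic gap. It might, but the decision would be made after seeing the data, and clinic would have to be considered in the first place. That is not a substitute for naming the term.

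**Conclusion.** The point holds as a minor design and analysis improvement. Sex is the only stated stratum, there are two clinics, and the primary model commits to neither factor. Depending on an unstated detail, the arm difference in clinic share has an SD from about 3 to about 8 points, against 2 to 2.5 with clinic-by-sex lists (50:50 clinics assumed). Near the upper end of the interleaved case, a 15-point gap moves the estimate by 0.03 to 0.075 SD if clinics differ by an assumed 0.2 to 0.5 SD.

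Three stronger readings should be resisted:
- The estimate is not biased: randomisation remains valid under every scheme considered.
- Separate lists would not remove clinic imbalance, because incomplete blocks leave a residue, and they are not strictly free.
- Stratified lists do not themselves buy the saving in participants; that comes from the clinic-by-time term in the model.

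**What to change.** In the Stage 1B overview, the Stage 1B randomisation paragraph and the assignment process (Section V, item 5.1), state that allocation is 1:1 in permuted blocks, stratified by clinic and sex. Generate four lists, and fill the two cabinets at each clinic from that clinic's own female and male lists. If this is already the intended practice, the change simply records it.

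In the analysis plan for the ACASI outcomes, prespecify clinic and sex, each with its interaction with time, in the primary model. These terms should not be left to the data-driven covariate rule.

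The cost is a few words in each place and two further lists from the same Stata routine. Overall arm sizes may be slightly less even, with a mean difference of about 2.5 to 3 participants. The loss of power is negligible, and the sample size stays at 160.
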